13.6 APPENDIX 6: SCHEDULE OF ASSESSMENTS AND PROCEDURES

Boxes marked with an X show what will happen at each visit.

Visit	Screening/ Randomization Day 1	In-Hospital Day 2	In-Hospital Day 3	Cardiologist Visit 1 (1 month)	Cardiologist Visit 2 (3 month)	Cardiologist Visit 3 (6 month)	Rehabilitation Specialist (6 month)
Length of time needed	30 minutes	N/A	N/A	1 hour	1 hour	1 hour	1 hour
Written informed consent	x						
Medical History	x			x	x	x	x
Vital Signs	x			x	x	x	x
Physical examination	x			x	x	x	x
Routine Hematology	x	x	x				
Routine Blood Chemistry	x						
ECG	x	x	x				
LV Function Test			x		x		
Endovascular Cooling Device	x	x	x				
Study Blood Sample Collection	x	x	x				
Review of Medications	x			x	x	x	x
Neuro- Psychological Assessment (Disability Rating Scale)							x
Clinical Outcomes/ Endpoints				x	x	x	x

13.7 APPENDIX 7: TIMI BLEEDING DEFINITION

Types of TIMI Bleeding

1. Major:
 - Any intracranial bleeding or;
 - Clinically overt signs of hemorrhage associated with a drop in hemoglobin (Hgb) of ≥ 5 g/dL. (or, when Hgb is not available, an absolute drop in hematocrit (Hct) of $\geq 15\%$).
2. Minor:
 - Any clinically overt signs of hemorrhage (including imaging) that is associated with a fall in Hgb of 3 to < 5 g/dL (or, when Hgb is not available, a fall in Hct of 9 to $\leq 15\%$).
3. Needing medical attention
 - Any overt sign of hemorrhage that requires medical evaluation, medical treatment (including discontinuation of medications), or surgical treatment, and that does not meet criteria for a major or minor bleeding event, as defined above.
4. Minimal
 - Any overt bleeding event that does not meet the criteria above

NOTE: To account for transfusions, Hgb measurements will be adjusted for any packed red blood cells (PRBCs) or whole blood given between baseline and post-transfusion measurements. A transfusion of one unit of blood will be assumed to result in an increase by 1 gm/dL in Hgb. Thus, to calculate the true change in hemoglobin, if there has been an intervening transfusion between two blood measurements, the following calculations should be performed: $\Delta \text{Hgb} = [\text{Baseline Hgb} - \text{Post transfusion Hgb}] + [\# \text{ transfused units}]$.

TIMI Clinically Significant Bleeding:

The presence of either TIMI major or TIMI minor bleeding, or bleeding requiring medical attention.

For patients experiencing a hemorrhage that occurs as a result of CABG, the following criteria will be used:

5. Bleeding in the Setting of Coronary Artery Bypass Graft Surgery (CABG)

Minor and minimal bleeding are not adjudicated in the setting of CABG

As a drop in hemoglobin and transfusions are commonplace in routine CABG cases, one of the following criteria must be met to qualify for major bleeding in any of the preceding definitions:

 - Fatal bleeding (i.e., bleeding that directly results in death)
 - Perioperative intracranial bleeding*
 - Reoperation following closure of the sternotomy incision for the purpose of controlling bleeding
 - Transfusion of ≥ 5 units of packed red blood cells (PRBCs) or whole blood within a 48 hour period. Cell saver transfusion will not be counted in calculations of blood products
 - Chest tube output > 2 L within a 24 hour period

*In light of the increased sensitivity of brain imaging for microhemorrhages of uncertain clinical significance, brain imaging with an incidental finding of microhemorrhage in the absence of associated clinical symptoms/ findings will not be considered to meet the protocol definition of intracranial hemorrhage.

Relationship of Bleeding to Death

Fatal Bleeding

Death in which a bleeding event directly led to death within 7 days. Examples of fatal bleeding events are an intracranial hemorrhage that led to herniation of the brain and death within 24 hours, and a massive gastrointestinal hemorrhage that results in shock, hemodynamic collapse, and death. If a bleeding event is considered fatal, then the cause of death must be either intracranial or non-intracranial bleeding.

Bleeding Contributed to Death

Death in which a bleeding event was part of a causal chain of medical events that ultimately led to death within 30 days of the bleed, but bleeding was not directly and/or immediately related to the subject's death. An example of bleeding contributing to death is a large retroperitoneal bleed that leads to surgical evacuation, development of a subsequent abscess in the area of bleeding that leads to sepsis, multiorgan failure, and death 10 days after the onset of bleeding. If bleeding has contributed to death (but the bleeding was not categorized as "fatal"), then the cause of death must be recorded as something other than intracranial / non-intracranial bleeding.

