6.2 Bleeding

Defined as TIMI minor or major (See Appendix 7).

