6.3 Stroke

A neurologic injury occurring as a result of a disease process involving one or more of the blood vessels of the brain, i.e. atherosclerosis, dissection, thrombus, embolism, decreased perfusion pressure resulting in inadequate blood flow, vessel rupture associated with intracranial haemorrhage. Strokes will be classified as hemorrhagic or non-hemorrhagic with duration > 24 hrs.

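### Outside CABG, a fatal extracranial bleed has no route of its own to TIMI major, and the stroke definition has no alternative for death within 24 hours; two secondary outcomes can miss or under-grade such events

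*Combined protocol and SAP*

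**What the plan says.** **Bleeding.** Section 6.2 defines the outcome: "Defined as TIMI minor or major (See Appendix 7". Section 5.2 item 3 counts minor and major together, during the first hospitalization plus 7 days. For bleeds not caused by CABG, Appendix 7 item 1 has two routes to major. The first is "Any intracranial bleeding or" and the second is "Clinically overt signs of hemorrhage associated with a drop in hemoglobin (Hgb) of" at least 5 g/dL. The second has a fallback: "when Hgb is not available, an absolute drop in hematocrit (Hct) of" at least 15%. Minor needs a haemoglobin fall of 3 to <5 g/dL. Overt bleeding below that which needs evaluation or treatment goes into a third grade that the outcome does not count.

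The CABG list in the same appendix does have a criterion for death: "Fatal bleeding (i.e., bleeding that directly results in death". The closing part of Appendix 7, on how bleeding relates to death, defines fatal bleeding as "Death in which a bleeding event directly led to death within 7 days". It uses the term to assign cause of death and links it to no TIMI grade.

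**Stroke.** Section 6.3 first defines stroke by mechanism, with no time limit. It then adds: "Strokes will be classified as hemorrhagic or non-hemorrhagic with duration > 24 hrs". It does not mention a patient who dies before 24 hours have passed.

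**The concern.** Bleeding and stroke are among the secondary outcomes that could show a specific harm of cooling to 31°C. A grade that rests on a measured laboratory fall needs a second blood sample, and a duration criterion needs a survivor. The most severe events are the ones most likely to lack both. The appendix is also inconsistent with itself: the same fatal bleed is major after CABG but may be minor, or not counted, otherwise. If the gap is left open, the classification of these few cases will be decided case by case after the events have occurred.

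**Working it through.** **Plan's own figure.** The only relevant one is the 170 per arm in Section 8.1. With rates of 50% and 35%, two-sided alpha 0.05 (sidedness is not stated; two-sided assumed) and 80% power:

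n = [1.96·√(2·0.425·0.575) + 0.8416·√(0.5·0.5 + 0.35·0.65)]² / 0.15² = (1.370 + 0.582)² / 0.0225 ≈ 169.3, so 170 per arm and 340 in total.

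This reproduces (power at 170 per arm is 80.2%). It is used below only as a denominator; nothing in this point changes it.

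**Bleeding.** Appendix 7 gives: adjusted fall = (baseline Hgb − post-transfusion Hgb) + units transfused. Applied to a fatal, extracranial, non-CABG bleed:

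| Measured fall (g/dL) | Units | Adjusted fall | Grade | In the outcome? |
|---|---|---|---|---|
| 2 | 0 | 2 | below minor | no |
| 2 | 1 or 2 | 3 or 4 | minor | yes, under-graded |
| 2 | 3 | 5 | major | yes |
| 0 | 2 | 2 | below minor | no |
| 0 | 3 or 4 | 3 or 4 | minor | yes, under-graded |
| 0 | 5 | 5 | major | yes |
| no repeat sample | any | not computable | none | no |

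So the event is lost only when the adjusted fall is below 3 g/dL or there is no repeat value. (Where only haematocrit is available, the equivalent is a fall below 9%.) Between 3 and <5 g/dL it is kept but ranked as minor. A fatal intracranial bleed is always major, whatever the haemoglobin or the time to death.

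**Stroke.** The 24-hour clause in Section 6.3 can be read in two ways:

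| Reading | Non-hemorrhagic, fatal within 24 h | Hemorrhagic, fatal within 24 h |
|---|---|---|
| Clause covers non-hemorrhagic only | not covered | covered |
| Clause covers both types | not covered | not covered |

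The left column fails on both readings. On the second reading, one of Appendix 7's own examples of fatal bleeding, a brain bleed with herniation and death inside a day, would be a TIMI major bleed but not a stroke.

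**Size.** The documents give no bleeding or stroke rate, so an expected number of lost events cannot be calculated. Per event: 1/170 = 0.6, 2/170 = 1.2 and 3/170 = 1.8 percentage points of one arm. The counts 1 to 3 are illustrations, not estimates.

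**The case against.** The best case against is that very few events can be affected, and that the deaths are recorded elsewhere.

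- A massive bleed in hospital will usually be transfused, and each unit adds 1 g/dL. Section 4.4 also requires a blood count at any overt bleeding. This stands: many such bleeds will reach minor or major. It does not help a patient who dies before transfusion or before the repeat sample.
- Every death counts in the primary outcome and in secondary outcome 1, is adjudicated blind (Section 10.2) and goes to the DSMC within 24 hours (Section 12.4). Appendix 7 also requires bleeding to be recorded as the cause of a fatal bleed. This stands too. But total mortality does not show that deaths were haemorrhagic, and no listed outcome uses the fatal-bleeding label. Appendix 7's broader category of clinically significant bleeding would catch these events, but no outcome uses that either.
- Adjudicators might upgrade a fatal bleed on judgement. Section 5.2 ties adjudication to the stated definitions, and nothing in the text allows an upgrade.
- The first sentence of Section 6.3 has no time limit, so an early fatal stroke arguably still meets it. That is a fair reading, but a non-hemorrhagic stroke of this kind then fits neither class in the second sentence. The wording needs settling either way.

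Two stronger readings are tempting. A reader might infer that rapidly fatal bleeds and strokes in general fall out of the safety outcomes. The documents do not support that: intracranial bleeds always count as major, falls of 3 to <5 g/dL still count as minor, and the stroke clause may not reach hemorrhagic stroke. A reader might also treat every fatal bleed without a 5 g/dL fall as lost. That is the wrong threshold, because the outcome combines minor and major.

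**Conclusion.** The gap is real in the text but narrow. Followed exactly, Appendix 7 leaves out a fatal extracranial, non-CABG bleed with an adjusted fall below 3 g/dL or no repeat sample, and ranks one with a fall of 3 to <5 g/dL as minor. Section 6.3 does not cover a non-hemorrhagic stroke that is fatal within 24 hours, and may not cover a hemorrhagic one.

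The effect is confined to two of the fifteen secondary outcomes. The primary outcome, mortality, sample size, alpha and power are untouched. The number of events at stake is unknown and probably small; that it is small is a judgement resting on the transfusion correction and the repeat blood count, not on a rate in the documents. The point is worth acting on because the cases affected are fatal ones and the correction is nearly free.

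The haematocrit bands also overlap: a fall of exactly 15% is both minor and major. Since either grade counts in the combined outcome, this alone would not justify a change.

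**What to change.** 1. In Appendix 7 item 1 (Major), add a third criterion: fatal bleeding, as already defined in the appendix's closing part (bleeding that leads directly to death, with the 7-day limit).
2. In Section 6.3, extend the duration condition so that it is also met by death within 24 hours of onset, and state whether the condition applies to non-hemorrhagic stroke only or to both types.
3. As tidying only, let the minor haematocrit band stop short of 15%.

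The cost is three wording changes, with no new data, visits or patients. They should be made before any unblinded analysis, so that the rule is set without knowledge of which arm the affected cases belong to.

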13.8 APPENDIX 8 – THE DISABILITY RATING SCALE (DRS)

TBI NATIONAL DATABASE COLLECTION FORM

Patient Name: _____ Date of Rating: _____

Name of Person Completing Form: _____

DISABILITY RATING SCALE:

Disability Rating Scale ratings to be completed within 72 hours after Rehab. Admission. And within 72 hours before Rehab. Discharge.

A. EYE OPENING:

- (0) Spontaneous
 (1) To Speech
 (2) To Pain
 (3) None

0-SPONTANEOUS: eyes open with sleep/wake rhythms indicating active arousal mechanisms, does not assume awareness.
1-TO SPEECH AND/OR SENSORY STIMULATION: a response to any verbal approach, whether spoken or shouted, not necessarily the command to open the eyes. Also, response to touch, mild pressure.
2-TO PAIN: tested by a painful stimulus.
3-NONE: no eye opening even to painful stimulation.

B. COMMUNICATION ABILITY:

- (0) Oriented
 (1) Confused
 (2) Inappropriate
 (3) Incomprehensible
 (4) None

0-ORIENTED: implies awareness of self and the environment. Patient able to tell you a) who he is; b) where he is; c) why he is there; d) year; e) season; f) month; g) day; h) time of day.
1-CONFUSED: attention can be held and patient responds to questions but responses are delayed and/or indicate varying degrees of disorientation and confusion.
2-INAPPROPRIATE: intelligible articulation but speech is used only in an exclamatory or random way (such as shouting and swearing); no sustained communication exchange is possible.
3-INCOMPREHENSIBLE: moaning, groaning or sounds without recognizable words, no consistent communication signs.
4-NONE: no sounds or communications signs from patient.

C. MOTOR RESPONSE:

- (0) Obeying
 (1) Localizing
 (2) Withdrawing
 (3) Flexing
 (4) Extending
 (5) None

0-OBEYING: obeying command to move finger on best side. If no response or not suitable by another command such as "move lips," "blink eyes," etc. Do not include grasp or other reflex responses.
1-LOCALIZING: a painful stimulus at more than one site causes limb to move (even slightly) in an attempt to remove it. It is a deliberate motor act to move away from or remove the source of noxious stimulation. If there is doubt as to whether withdrawal or localization has occurred after 3 or 4 painful stimulations, rate as localization.
2-WITHDRAWING: any generalized movement away from a noxious stimulus that is more than a simple reflex response.
3-FLEXING: painful stimulation results in either flexion at the elbow, rapid withdrawal with abduction of the shoulder or a slow withdrawal with adduction of the shoulder. If there is confusion between flexing and withdrawing, then use pinprick on hands.
4-EXTENDING: painful stimulation results in extension of the limb.
5-NONE: no response can be elicited. Usually associated with hypotonia. Exclude spinal transection as an explanation of lack of response; be satisfied that an adequate stimulus has been applied.

D. FEEDING (COGNITIVE ABILITY ONLY)

- (0.0) Complete
 (1.0) Partial
 (2.0) Minimal
 (3.0) None

Does the patient show awareness of how and when to perform this activity? Ignore motor disabilities that interfere with carrying out this function. (This is rated under Level of Functioning described below.)
0-COMPLETE: continuously shows awareness that he knows how to feed and can convey unambiguous information that he knows when this activity should occur.
1-PARTIAL: intermittently shows awareness that he knows how to feed and/or can intermittently convey reasonably clearly information that he knows when the activity should occur.
2-MINIMAL: shows questionable or infrequent awareness that he knows in a primitive way how to feed and/or shows infrequently by certain signs, sounds, or activities that he is vaguely aware when the activity should occur.
3-NONE: shows virtually no awareness at any time that he knows how to feed and cannot convey information by signs, sounds, or activity that he knows when the activity should occur.

E. TOILETING (COGNITIVE ABILITY ONLY)

- (0.0) Complete
 (1.0) Partial
 (2.0) Minimal
 (3.0) None

Does the patient show awareness of how and when to perform this activity? Ignore motor disabilities that interfere with carrying out this function. (This is rated under Level of Functioning described below.) Rate best response for toileting based on bowel and bladder behavior
0-COMPLETE: continuously shows awareness that he knows how to toilet and can convey unambiguous information that he knows when this activity should occur.
1-PARTIAL: intermittently shows awareness that he knows how to toilet and/or can intermittently convey reasonably clearly information that he knows when the activity should occur.
2-MINIMAL: shows questionable or infrequent awareness that he knows in a primitive way how to toilet and/or shows infrequently by certain signs, sounds, or activities that he is vaguely aware when the activity should occur.
3-NONE: shows virtually no awareness at any time that he knows how to toilet and cannot convey information by signs, sounds, or activity that he knows when the activity should occur.

F.GROOMING (COGNITIVE ABILITY ONLY)

- (0.0) Complete
- (1.0) Partial
- (2.0) Minimal
- (3.0) None

Does the patient show awareness of how and when to perform this activity? (Ignore motor disabilities that interfere with carrying out this function. (This is rated under Level of Functioning described below.) Grooming refers to bathing, washing, brushing of teeth, shaving, combing or brushing of hair and dressing.

0-COMplete: continuously shows awareness that he knows how to groom self and can convey unambiguous information that he knows when this activity should occur.

1-PARTIAL: Intermittently shows awareness that he knows how to groom self and/or can intermittently convey reasonably clearly information that he knows when this activity should occur.

2-MINIMAL: shows cue sensitive or infrequent awareness that he knows in a primitive way how to groom self and/or shows infrequently by certain signs, sounds, or activities that he is vaguely aware when the activity should occur.

3-NONE: shows virtually no awareness at any time that he knows how to groom self and cannot convey information by signs, sounds, or activity that he knows when the activity should occur.

G.LEVEL OF FUNCTIONING (PHYSICAL, MENTAL, EMOTIONAL OR SOCIAL FUNCTION)

- (0.0) Completely Independent
- (1.0) Independent in special environment
- (2.0) Mildly Dependent-Limited assistance (non-resid - helper)
- (3.0) Moderately Dependent-moderate assist (person in home)
- (4.0) markedly Dependent-assist all major activities, all times
- (5.0) Totally Dependent-24 hour nursing care.

0-COMpletely INDEPENDENT: able to live as he wishes, requiring no restriction due to physical, mental, emotional or social problems.

1-INDEPENDENT IN SPECIAL ENVIRONMENT: capable of functioning independently when needed requirements are met (mechanical aids)

2-MILDLY DEPENDENT: able to care for most of own needs but requires limited assistance due to physical, cognitive and/or emotional problems (e.g., needs non-resident helper).

3-MODERATELY DEPENDENT: able to care for self partially but needs another person at all times. (person in home)

4-MARKEDLY DEPENDENT: needs help with all major activities and the assistance of another person at all times.

5-TOTALLY DEPENDENT: not able to assist in own care and requires 24-hour nursing care.

H."EMPLOYABILITY"(AS A FULL TIME WORKER, HOMEMAKER, OR STUDENT)

- (0.0) Not Restricted
- (1.0) Selected Jobs, competitive
- (2.0) Sheltered workshop, Non-competitive
- (3.0) Not Employable

0-NOT RESTRICTED: can compete in the open market for a relatively wide range of jobs commensurate with existing skills; or can initiate, plan, execute and assume responsibilities associated with homemaking; or can understand and carry out most age relevant school assignments.

1-SELECTED JOBS, COMPETITIVE: can compete in a limited job market for a relatively narrow range of jobs because of limitations of the type described above and/or because of some physical limitations, or can initiate, plan, execute and assume many but not all responsibilities associated with homemaking, or can understand and carry out many but not all school assignments.

2-SHELTERED WORKSHOP, NON-COMPETITIVE: cannot compete successfully in a job market because of limitations described above and/or because of moderate or severe physical limitations; or cannot without major assistance initiate, plan, execute and assume responsibilities for homemaking; or cannot understand and carry out even relatively simple school assignments without assistance.

3-NOT EMPLOYABLE: completely unemployable because of extreme psychosocial limitations of the type described above, or completely unable to initiate, plan, execute and assume any responsibilities associated with homemaking; or cannot understand or carry out any school assignments.

The psychosocial adaptability or "employability" item takes into account overall cognitive and physical ability to be an employee, homemaker or student.

This determination should take into account considerations such as the following:

1. Ability to understand, remember and follow instructions.
2. Can plan and carry out tasks at least at the level of an office clerk or in simple routine, repetitive industrial situation or can do school assignments.
3. Ability to remain oriented, relevant and appropriate in work and other psychosocial situations.
4. Ability to get to and from work or shopping centers using private or public transportation effectively.
5. Ability to deal with number concepts.
6. Ability to make purchases and handle simple money exchange problems.
7. Ability to keep track of time and appointments.

13.9 APPENDIX 9 –
THE UNIVERSITY OF OTTAWA HEART INSTITUTE AND
THE OTTAWA HOSPITAL THERAPEUTIC HYPOTHERMIA PROTOCOL

 
EMERGENCY DEPARTMENT PHYSICIAN'S ORDERS ORDONNANCES MÉDICALES
	
 Civic  General-Général	
Medication Allergies / Reaction  none known –aucune connue	Substances or Food Allergies / Reactions  none known –aucune connue
NON-MEDICATION – SANS MÉDICAMENTS Init.	I.V. & MEDICATION-SOLUÉ & MÉDICAMENTS (Medic., dose-posologie, route-voie, frequency-fréquence) Init.
ED Therapeutic Hypothermia Post Cardiac Arrest	

Inclusion Criteria:
 
 Greater than 18 years of age Witnessed cardiac arrest from ventricular fibrillation or non-perfusing ventricular tachycardia Return of spontaneous circulation (ROSC) without full neurological recovery not attributed to sedation 
Exclusion Criteria:
 
 Greater than 30 min from arrest to ACLS Greater than 60 min from arrest to return of spontaneous circulation (ROSC) Refractory shock (MAP less than 60 mmHg for greater than 30 min after ROSC despite vasopressors) Refractory hypoxia (O₂ sats less than 85% for more than 15 min after ROSC despite adequate ventilation) Severe coagulopathy with clinical evidence of bleeding 
Goals:
 
 Priority transfer to ICU or CCU for definitive management Start active cooling measures within 2 hours after ROSC Decrease core temperature to 34C but not lower than 34C in the Emergency Department 
NON-MEDICATION INVESTIGATIONS/TREATMENTS Do not Delay PCI for cooling measures
 
 Call a CODE STEMI if meets STEMI criteria 
 Institute STEMI protocol in parallel with cooling Call a CODE ROSC if patient does not meet STEMI criteria, but is a candidate for cooling 
Monitoring:
 
 Continuous cardiac and core temperature monitoring Vital signs q 5 minutes Baseline QTC measurement and q4h Baseline neuro vital signs and q 1h Maintain SaO₂ greater than 92% and MAP 65 mmHg Monitor for shivering and seizure activity 
Investigations:
 
 12 lead ECG stat (consider 15 lead) CBC, Na, K, Cl, CO₂, urea, Cr, Glu, CK, cTnl, pt, INR, anti Xa, Ca, Mg, PO₄, AST, ALT, lipase, bilirubin, ABG 
Treatment:
 
 Intubation and mechanical ventilation on a rate Foley catheter with temperature sensor Nasopharyngeal temperature probe Apply ice packs to head, neck, axilla, groin and proximal limbs or cooling blanket set to 34 C. Rotate ice packs q 20 min and do skin checks q2h Patient should remain minimally covered Hold cooling measures if temperature less than 34C Notify MD if temperature is less than 33C 	
IV & MEDICATION (Medic., dose, route, frequency)
 
Patient's weight kg _____
 
IV THERAPY:
 
 1 IV Normal Saline at _____ml/ hour Use room temperature IV fluids 
SEDATION
 
  Midazolam (Versed) 
 Midazolam (Versed) 1-2 mg IV bolus. Repeat q 5 min for agitation (Max 10 mg/hr). Consider propofol (Diprivan) if greater than 10mg/ hour required for sedation.  Propofol (Diprivan) 
 Vasopressor support may be required to maintain adequate MAP when propofol is administered Administer propofol (Diprivan) 10 - 20 mg IV bolus Start propofol (Diprivan) infusion at 0.3 mg/kg/hr Titrate infusion q 5 min to Riker score* of ____ and minimum MAP of 65 mmHg. (max. infusion rate 3 mg/kg/hr) Monitor BP q 2 min during titration. Evaluate Riker score* q1h and pm, and adjust infusion accordingly. propofol (Diprivan) 10-20 mg IV bolus pm for agitation (Max 60 mg/hr) 
Refer to propofol (Diprivan) infusion chart
 
ANALGESIA
 
  Fentanyl 
 Administer fentanyl 50 mcg IV bolus Start fentanyl infusion at 1 mcg/kg/hr Titrate infusion q 15 minutes and minimum MAP of 65 mmHg. Fentanyl 25-50 mcg IV bolus pm (Max. ____ mcg/hr) 
Refer to fentanyl infusion chart
 
PARALYSIS ONLY TO SUPPRESS SHIVERING
 
Ensure adequate sedation. Patient must be intubated and ventilated on a rate.
 
  Rocuronium ____mg IV bolus over 5 - 15 seconds (Recommended initial dose 0.6 mg/kg). Max 50mg
